The primary objective of this feasibility study is to collect preliminary information to aid in the design and conduct of future trials evaluating the safety and efficiency of a novel mask (nasal reservoir cannula) plus standard nasal cannula vs. standard nasal cannula alone for supplemental oxygen delivery in the treatment of hospitalized pediatric patients with hypoxemia due to severe pneumonia. This study is intended to provide information on intervention delivery and implementation, trial conduct, availability of patients and recruitment rates, protocol adherence, and effect sizes and outcomes to guide power calculation and design of a more definitive future study.

Our long-term goal is to conduct definitive studies to evaluate whether the addition of a novel mask (nasal reservoir cannula) to a standard nasal cannula during supplemental oxygenation is safe and more efficient (compared with a standard nasal cannula alone) in reducing the total amount of oxygen needed per cylinder for adequate oxygen delivery in pediatric patients with hypoxemic respiratory illness in resource-limited settings.

Study Design:

The study is an open-label, prospective, feasibility study of hospitalized pediatric patients with hypoxemia due to severe pneumonia. Following study eligibility, patients will receive baseline assessments followed by supplemental oxygen per standard of care before being equally randomized to one of the following two groups:

- Group A: Each patient will receive oxygen for 1 hr using a novel mask (nasal reservoir cannula) plus standard nasal cannula (Period 1), followed by a 1-hr period of continued use of the standard nasal cannula delivery (Period 2).
- Group B: Each patient will receive oxygen for 1 hr using a standard nasal cannula (Period 1), followed by a 1-hr period of continued use of the novel mask (nasal reservoir cannula) plus standard nasal cannula (Period 2).

Summary of Subject Eligibility Criteria:

Inclusion Criteria:

- Age ≥ 1 year and ≤ 6 years of age.
- Severe pneumonia based on World Health Organization (WHO) criteria.

- SpO₂ \geq 85% and < 94% by pulse oximetry on room air.
- Hospital admission based on clinician judgment.
- Written informed consent from parent(s)/guardian(s) of subjects must be obtained before any study procedure is performed.
- Body weight $\geq 8 \text{ kg}$ and $\leq 26 \text{ kg}$

Exclusion Criteria:

- Hypercapnia (pCO₂ > 55 mm Hg or 7.32 kPa) on room air
- Acidosis / lactic acidosis (pH < 7.20 and/or lactate > 3 mmol/L) on room air
- SpO₂ < 85% or \geq 94% by pulse oximetry on room air
- SICK score > 2.4
- Hemoglobin < 7 g/dL
- Facial abnormalities or trauma precluding use of nasal prongs.
- Requirement of intubation or noninvasive or invasive positive-pressure ventilation.
- Suspected or known pneumothorax.
- Body weight < 8 kg and > 26 kg
- Hemodynamic instability based on clinician judgment.
- SpO₂ < 90% by pulse oximetry on oxygen, measured at the end of the enrollment and before initiation of Period 1.

Investigational Device:

Mask (nasal reservoir cannula)

Procedures:

- All patients will receive standard of care for their underlying disease according to World Health Organization (WHO) recommendations, including availability of standardized care of oxygen therapy.
- Safety evaluations will consist of vital signs (respiratory rate, temperature, blood pressure, heart rate), physical examination, clinical laboratory, and adverse event information. Clinical laboratory tests for safety assessment will include metabolic panels, complete blood count, continuous transdermal end-tidal carbon dioxide (CO₂) monitoring, blood gases (P_aO₂, P_aCO₂, pH, base excess), peripheral blood oxygen saturation (SpO₂), and blood lactate.
- Efficacy will be measured throughout the hospitalization by continuous monitoring of transdermal end-tidal carbon dioxide (CO₂), blood gases (P_aO₂, P_aCO₂, pH, base excess), peripheral blood oxygen saturation (SpO₂), and blood lactate. Signs of inflammation in children that can kill (SICK) score will be calculated from physical

- exam and SpO_2 data. The amount of oxygen used from a cylinder during Period 1 through 2 will be measured.
- At screening, severe pneumonia by WHO criteria, peripheral blood oxygen saturation (SpO₂ by pulse oximetry) on air, capillary blood gas with lactate to evaluate for hypercapnia/acidosis, hemoglobin (rapid) and complete blood count (CBC) to evaluate for anemia / leukocytosis, SICK score to evaluate degree of illness, and body weight will be obtained to determine study eligibility.
- Baseline (pre-treatment): Once eligibility criteria are met, physical examination, including vital signs and capillary refill time; blood glucose (point of care); malaria rapid diagnostic test; and concomitant medication information will be obtained. In addition, a metabolic panel will be recorded *only* if obtained as standard of care. Any baseline assessment obtained during the screening period will be used as the baseline value. Patients will be placed on supplemental oxygen consistent with standard of care. Based on the body weight of the patients the size (small or large) of the nasal reservoir cannula to be used during the intervention periods will be determined.
- Period 1 (Group A: nasal reservoir cannula plus nasal cannula for 1 hr, Group B: standard nasal cannula alone) will include:

Period 1 (1 hr):

- Continuous monitoring of transdermal end-tidal carbon dioxide (CO₂) with recording every 15 min.
- Continuous monitoring of SpO₂ by pulse oximetry with recording every 15 min.
- Record vital signs every 15 min.
- Record oxygen flow (L/min) every 15 min.
- Record concomitant medication information.
- Record adverse events.

End of Period 1:

- Physical examination, including capillary refill time; capillary blood gases (P_aO₂, P_aCO₂, pH, base excess, lactate); and SICK score.
- Period 2 (Group A: nasal cannula for 1 hr, Group B: nasal reservoir cannula with standard nasal cannula alone) will include:

Period 2 (1 hr):

- Continuous monitoring of transdermal end-tidal carbon dioxide (CO₂) with recording every 15 min.
- Continuous monitoring of SpO₂ by pulse oximetry with recording every 15 min.
- Record vital signs every 15 min.

- Record oxygen flow (L/min) every 15 min.
- Record concomitant medication information.
- Record adverse events.

End of Period 2:

- Physical examination, including capillary refill time; capillary blood gases (P_aO₂, P_aCO₂, pH, base excess, lactate); and SICK score.
- Study duration is from the beginning of Period 1 to end of Period 2 (approximately 2 hour).

Sample Size and Number of Sites:

• The target sample size for the study (up to 20 patients) is consistent with feasibility studies for other clinical interventions. Planned number of sites: 1 (Department of Pediatrics, Makerere University, Kampala, Uganda).

Removal of Subjects from Investigational Study Treatment or Assessment:

1 LIST OF ABBREVIATIONS

ABBREVIATION DEFINITION

AE adverse event

ALT alanine transaminase
AST aspartate transaminase
BUN blood urea nitrogen
CBC complete blood count

CO₂ carbon dioxide

CRF case reporting form

dL deciliter

FiO₂ fraction of inspired oxygen GCP Good Clinical Practice

HIPAA Health Insurance Portability and Accountability Act

hr hour(s)

IEC Institutional Ethics Committee
IRB Institutional Review Board

ITT intent-to-treat kg kilogram kPa kilopascals

MCV mean corpuscular volume

mg milligram min minutes

mm Hg millimeters mercury

 O_2 oxygen

PCO₂ Partial pressure of carbon dioxide in arterial blood

Partial pressure of carbon dioxide in blood

PO₂ Partial pressure of oxygen in blood

P_aO₂ Partial pressure of oxygen in arterial blood

RBC Red blood cell

SAE serious adverse event

SpO₂ peripheral capillary oxygen saturation

SICK Signs of inflammation in children that can kill UNICEF United Nations Children's Emergency Fund

WHO World Health Organization

2 INTRODUCTION

2.1 Pediatric Respiratory Illness and Hypoxemia in the Developing World

Pneumonia is the leading infectious cause of death among children less than 5 years of age (Liu et al., 2015). Estimates indicate that 922,000 children died from pneumonia in 2015, accounting for 15% of all deaths of children under 5 years of age (World Health Organization 2015). Hypoxemia is a major fatal complication of pneumonia, and the risk of death increases with increasing severity of hypoxemia (Djelantik et al., 2003).

Childhood pneumonia can be especially difficult to diagnose and treat in low-resource settings, and is the leading cause of death among children under 5 years in the developing world (Ginsberg et al., 2015). Indeed, more than half of the world's annual new pneumonia cases are concentrated in just five countries where 44% of the world's children aged less than 5 years live: India (43 million), China (21 million) and Pakistan (10 million) and in Bangladesh-Indonesia and Nigeria (6 million each) (World Health Organization 2016a). Major risk factors for childhood pneumonia in the developing world include malnutrition, low birth weight (≤ 2500 g), non-exclusive breastfeeding (during the first 4 months of life), lack of measles immunization (within the first 12 months of life), indoor air pollution, and crowding. These factors also contribute to other respiratory and systemic illnesses that result in hypoxemia. The main bacterial causes of clinical pneumonia in developing countries are *S. pneumoniae* and *Haemophilus influenzae type b*, and the main viral cause is respiratory syncytial virus, but estimates of their relative importance vary in different settings.

In low-resource settings, early detection of pneumonia or other hypoxemic respiratory illness, identification of a pathogen, and initiation of treatment is challenging but potentially life-saving. In particular, hypoxemia is a common and potentially lethal complication of acute respiratory infection in children in resource-poor settings, especially among those with severe disease. In these settings, hypoxemia can also occur in children with illnesses of infectious origin that are not primarily due to lower respiratory tract infection, such as acute sepsis, meningitis, and severe malaria, or due to different forms of shock syndrome such as hypovolemic shock due to diarrhea, trauma, and cardiac conditions. In developing countries, instruments for measuring arterial oxygen saturation are not available in most settings, which complicate the ability of health providers to detect hypoxemia in children with acute respiratory infections. In these situations, clinical signs are used to guide the initiation and use of oxygen therapy (World Health Organization 2016b). Besides availability of instruments to measure oxygenation, oxygen delivery systems for neonate and pediatric patients with hypoxemia are a critical resource as mainstay of treatment. However, oxygen supplies are also unavailable or inadequate throughout much of the developing world (Duke et al., 2006). In the setting of resourcepoor hospitals, the cost, maintenance, local availability of compressed air (for oxygen cylinders), power, and logistics remain challenges for the adequate care of pediatric hypoxemic patients (Coghill et al., 2011). The critical necessity of providing better access to quality and sustainable uninterrupted oxygen systems is underscored by their impact and cost-effectiveness, which compares favorably with other higher profile child survival interventions such as new vaccines (Duke et al., 2010).

2.2 Limitations of Oxygen Delivery in the Developing World

Deficiencies in the delivery and sustainability of oxygen to hypoxemic infants and children vary significantly in the developing world (Catto et al., 2011). Oxygen cylinders, which contain the gas in compressed form, are the standard storage form of oxygen in most poorly resourced or remote health facilities. Cylinders do not require an electrical supply but are expensive, difficult to transport, and require regular replenishment (Duke et al., 2010). In contrast, oxygen concentrators are machines that can concentrate oxygen at the bedside by absorption of nitrogen from atmospheric air; they are a less expensive and more reliable alternative for providing oxygen treatment, as long as there is an ability to maintain them and a reliable power supply (World Health Organization 2016b). Central piped oxygen is impractical for most hospitals in resource-limited countries.

Regardless of the source of oxygen, methods of delivery to the patient also vary but ideally should be safe, simple, effective, and inexpensive (World Health Organization 2016b). Nasal prongs (also called cannula) and nasal or face masks are the most efficient means of delivery of oxygen to balance safety and efficacy for long-term oxygen delivery in hypoxemic patients. Standard flow rates for oxygen through nasal prongs or nasal catheters are 0.5-1 L/min for neonates, 1-2 L/min for infants, and 1-4 L/min for older children (World Health Organization 2016b).

Methods of oxygen conservation (termed "oxygen conserving devices") have included both changing the interface (e.g., reservoir cannulas and transtracheal catheters) and changing the oxygen delivery system. Reservoir cannulas, a more common oxygen-conserving device, function by storing oxygen in the reservoir space during exhalation, making that oxygen available as a bolus upon the onset of the next inhalation (Soffer et al., 1985; Tiep and Carter, 2016). Oxygen is conserved because the patient breathes a higher concentration of oxygen without increasing flow from the oxygen tank or concentrator. Reservoir cannulas increase the percent of oxygen in the air that the patient inhales over that delivered by standard nasal cannula and usually enable a reduction in the oxygen flow setting of approximately 25 to 50 percent while maintaining the same pulse oxygen saturation. The development of oxygen conserving devices was based on efforts to improve the portability of oxygen therapy by reducing the liter flow and thereby enabling patients to use a smaller and lighter ambulatory system, or a standard system for longer time periods (Hofmann 1994). Other advantages include a reduction of overall costs of long-term oxygen therapy and the ability to treat refractory hypoxemia more effectively.

Tables 1 and 2 show typical gas, liquid, and concentrator oxygen systems – and oxygen-conserving devices (American Thoracic Society 2015), many of which are not readily available or practical in resource-limited settings.

Table 1. Gas, Liquid and Concentrator Oxygen Systems

Features	Concentrator	Cylinder (Compressed Gas)	Liquid

Reliability	Good with regular maintenance	Good but gauges may become inaccurate	Generally good but connector may freeze
Cost	Least expensive but cost of electricity born by patient	Higher	Highest
Powerwall current	Required	Not required	Not required
Transfilling	Good only on special units that allow transfilling	Limited	Excellent
Ambulatory use	Good with transfill systems to gas plus conserver	Good with conserver	Good alone and with conserver
Stationary weight	35-50 lb	H cylinder 200 lb	Reservoir 120 lb
Use time at 2 L⋅min ⁻¹	Continuous	2.5 days	8.9 days, special system >30 days
Portable weight	Portable units are not presently available	E cylinder 22 lb with cart	6 lb with no conserver
Use time at 2 L⋅min ⁻¹	Unlimited	5 h	4 h
Portable weight with conserver	See gas transfill portable with conserver	M6 cylinder 4.5 lb	3.4 lb with conserver
Use time at 2 L⋅min ⁻¹	See gas transfill portable with conserver	12 h	10 h

Table 2. Comparison of Oxygen-Conserving Devices

Conserving **Reservoir Cannula Demand Pulse Transtracheal Catheter Device Delivery** Conserving method Early inspiration Store during exhalation Store at end exhalation; bypass upper airway dead space delivery Efficiency gain ¹ 2:1-7:1 2:1-3:1 2:1-4:1 (savings) Good Mechanically complex Mucus plug possible Reliability Comfort Adequate-good Good Adequate-good Cosmetics Obtrusive Adequate Best Cost Low Higher Highest Most efficient Cosmetics Unique advantages Inexpensive Easy initiation No nasal/ear irritation Alarms programmable Reliable Good compliance Mechanically complex Disadvantages Bulky on face Special care + training Poor performance for Failure is possible Surgical complications Mucus plugs pediatric patients Poor performance for pediatric patients

[figure not shown]
2.3 Global Good/Intellectual Ventures Pediatric Mask (Nasal Reservoir Cannula)

Improving oxygen delivery and extending oxygen supplies to ill patients with respiratory distress can reduce fatalities in resource-poor settings. Global Good has developed a low cost oxygen mask (nasal reservoir cannula) to more efficiently deliver oxygen to the pediatric patient by increasing dead space to recapture a portion of expelled oxygen using

¹ Efficiency gain is based on adult patients. Most conserving devices are not approved for pediatric use.

[figure not shown]
the spatial distribution of the nasal reservoir cannula volume and length of surface seal. This nasal reservoir cannula fits over a standard nasal cannula (also termed prong) (see Fig. 1 below). The system is designed to reduce administered oxygen to deliver an equal or higher fraction of inspired oxygen (FiO₂) per oxygen delivered (L/min) compared with a standard nasal cannula alone. Please refer to the device brochure (Appendix I) for instructional details on the nasal reservoir cannula.

Figure 1. Novel Nasal Reservoir Cannula

[figure not shown]
Mask performance was evaluated using a breathing simulator developed at the Global Good Laboratory (Bellevue, WA). The system consists of a breathing simulator (ASL 5000, IngMar Medical, Pittsburgh, PA) paired with an anatomically correct airway and face constructed by 3D printing computerized tomography scan data (Fig. 2). Carbon dioxide was titrated into the lung to simulate metabolism. The end-tidal carbon dioxide (CO₂), which is equivalent to the maximal concentration of carbon dioxide at the end of an exhaled breath, and FiO₂ were measured. An array of breathing waveforms was tested to bound mask performance.

Figure 2. Pediatric Breathing Simulator

For hospitalized patients with hypoxic respiratory illnesses, the minimal oxygen delivered recommended by the World Health Organization (WHO) is in ranges typically used in low-flow nasal cannulas; in vitro experiments on the breathing simulator indicate that the novel nasal reservoir cannula may be able to provide the same or higher FiO₂ at approximately 2.5-times lower oxygen flow rate (L/min) compared with a standard nasal cannula alone (Global Good, data on file; see Fig. 3). This can result in less oxygen used than conventional delivery systems, which may be valuable for resource limited settings where oxygen supplies are limited.

Figure 3 Oxygen Flow and FiO₂ of Novel Mask (Nasal Reservoir Cannula)

3 OBJECTIVES

The primary objective of this feasibility study is to collect preliminary information to aid in the design and conduct of future trials evaluating the safety and efficiency of a novel mask (nasal reservoir cannula) plus nasal cannula vs. nasal cannula alone for supplemental oxygen delivery in the treatment of hospitalized pediatric patients with hypoxemia due to severe pneumonia. This study is intended to provide information on intervention delivery and implementation, trial conduct, availability of patients and recruitment rates, protocol adherence, and effect sizes and outcomes to guide power calculation and design of a more definitive future study.

Our long-term goal is to conduct definitive studies to evaluate whether the addition of a novel mask (nasal reservoir cannula) to a standard nasal cannula during supplemental oxygenation is safe and more efficient (compared with standard nasal cannula alone) in reducing the total amount of oxygen needed per cylinder for adequate oxygen delivery in pediatric patients with hypoxemic respiratory illness in resource-limited settings.

4 INVESTIGATIONAL PLAN

4.1 Summary of Study Design

The study is an open-label, prospective, feasibility study of hospitalized pediatric patients \geq 1 year and \leq 6 years of age with hypoxemia due to severe pneumonia. The primary objective of this feasibility study is to collect preliminary information to aid in the design and conduct of future trials evaluating the safety and efficiency of a novel mask (nasal reservoir cannula) plus standard nasal cannula vs. standard nasal cannula alone for supplemental oxygen delivery in the treatment of hospitalized pediatric patients with hypoxemia due to pneumonia in resource-poor settings. This study is intended to provide valuable information on the intervention delivery and implementation, trial conduct, availability of patients and recruitment rates, protocol adherence, and effect sizes and outcomes to guide power calculation and design of a more definitive future study.

Patients meeting entry criteria will receive baseline assessments followed by supplemental oxygen per standard of care. Patients will then be equally randomized to one of the two following groups:

- Group A: Each patient will receive oxygen for 1 hr using a novel mask (nasal reservoir cannula) plus standard nasal cannula (Period 1), followed by a subsequent 1-hr period of continued use of the standard nasal cannula delivery (Period 2).
- Group B: Each patient will receive oxygen for 1 hr using a standard nasal cannula (Period 1), followed by a 1-hr period of continued use of the novel mask (nasal reservoir cannula) plus standard nasal cannula (Period 2).

Patients with a body weight of 8-13 kg will receive treatment with a small 30 ml mask and patients with a body weight of 14-26 kg will receive treatment with a large 50 ml mask.

[figure not shown]
Safety evaluations will consist of vital signs (respiratory rate, temperature, blood pressure, heart rate), physical examination, clinical laboratory, and adverse event information. Clinical laboratory tests for safety assessment will include hemoglobin (rapid) and complete blood count; capillary blood gases (at screening and 2 time points during the study) to evaluate P_aO₂, P_aCO₂, pH, base excess, lactate; continuous oxygen saturation (SpO₂) and transdermal end-tidal carbon dioxide (CO₂) monitoring; blood glucose (point of care); malaria rapid diagnostic test; and results of comprehensive metabolic panels for patients in whom these are clinically indicated and obtained as part of routine care.

Efficacy will be measured throughout the hospitalization by continuous monitoring of transdermal end-tidal CO₂, capillary blood gases (P_aO₂, P_aCO₂, pH, base excess, lactate), and peripheral blood oxygen saturation (SpO₂). Signs of inflammation in children that can

kill (SICK) score will be calculated from physical exam and SpO₂ data. The amount of oxygen used from a cylinder during Period 1 through 2 will be measured.

The study design is illustrated below.

Figure 4. Illustration of Study Design

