4.2.1.1 Screening Evaluations

The following screening assessments must be done to determine eligibility for study participation. Written consent from parents(s)/guardian(s) will be obtained before conducting any study procedures.

- Screen for age and weight entry criteria (see Section 5).
- Medical history.
- Physical examination including body weight.
- Severe pneumonia (based on WHO criteria).
- Peripheral blood oxygen saturation (SpO₂) by pulse oximetry on air.
- Capillary blood gas with lactate (P_aO₂, P_aCO₂, pH, base excess, lactate) to evaluate for acidosis and hypercapnia.
- Completion of SICK score form (based on physical exam and SpO₂) data.
- Rapid hemoglobin and complete blood count (CBC).

- Malaria rapid diagnostic test.
- Point of care blood glucose.
- Comprehensive metabolic panel will be obtained *only* if indicated as part of standard care.

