4.2.1.2 Baseline (Pre-treatment) Evaluations

Once eligibility criteria are met, baseline assessments are obtained. Any baseline assessment obtained during the Screening period will be used as the baseline value.

- Vitals signs and capillary refill time.
- Record concomitant medication information.
- Determine mask size to be used in line with body weight. Patients with a body weight of 8-13 kg will receive treatment with a small 30 ml mask and patient with a body weight of 14-26 kg will receive treatment with a large 50 ml mask.
- Peripheral blood oxygen saturation (SpO₂) by pulse oximetry on oxygen.

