6.1 Inclusion Criteria

Patients may be included in the study only if they meet **all** of the following criteria:

- [1] Age ≥ 1 and ≤ 6 years.
- [2] Severe pneumonia based on WHO criteria (see Appendix B).
- [3] SpO₂ \geq 85% and < 94% by pulse oximetry on room air.
- [4] Hospital admission based on clinician judgment.
- [5] Written informed consent from parent(s)/guardian(s) of subjects must be obtained before any study procedure is performed.
- [6] Body weight $\geq 8 \text{ kg and } \leq 26 \text{ kg}$

Exclusion Criteria:

Patients meeting any of the following criteria will not be eligible to participate in the study:

- [1] Hypercapnia (pCO₂ > 55 mm Hg or 7.32 kPa) on room air
- [2] Acidosis / lactic acidosis (pH <7.20 and/or lactate >3 mmol/L) on room air
- [3] SpO₂ < 85% or \geq 94% by pulse oximetry on room air
- [4] SICK score > 2.4
- [5] Hemoglobin < 7 g/dL
- [6] Facial abnormalities or trauma precluding use of mask and nasal prongs.
- [7] Requirement of intubation or noninvasive or invasive positive-pressure ventilation.
- [8] Suspected or known pneumothorax.
- [9] Body weight $\leq 8 \text{ kg and} \geq 26 \text{ kg}$
- [10] Hemodynamic instability based on clinician judgment.
- [11] $SpO_2 < 90\%$ by pulse oximetry on oxygen, measured at the end of the enrollment and before initiation of Period 1.

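### The written sequence starts oxygen only after consent, screening and baseline assessments, although children at room-air SpO2 85–89% can be enrolled and Appendix B calls for oxygen below 90%

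*Protocol*

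**What the plan says.** Section 4.1 gives the order as "Patients meeting entry criteria will receive baseline assessments followed by supplemental oxygen per standard of care", with randomization next. The synopsis (Study Design) agrees: "Following study eligibility, patients will receive baseline assessments followed by supplemental oxygen per standard of care before being equally randomized". Section 5 likewise gives oxygen to patients who meet the entry criteria.

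Eligibility itself sits behind a list. Section 4.2.1.1 states "The following screening assessments must be done to determine eligibility for study participation" and "Written consent from parents(s)/guardian(s) will be obtained before conducting any study procedures". The list includes history, examination, SpO2 on air, capillary gas with lactate, the SICK form, rapid hemoglobin and full blood count, malaria test and glucose. A metabolic panel is added only if standard care calls for it.

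The synopsis places some of these under baseline instead: "Once eligibility criteria are met, physical examination, including vital signs and capillary refill time; blood glucose (point of care); malaria rapid diagnostic test". Later in that same paragraph comes "Patients will be placed on supplemental oxygen consistent with standard of care". That sentence appears again, word for word, under Period 1 in Section 4.2.2.1.

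The saturation range for entry is "85% and < 94% by pulse oximetry on room air" at or above the lower bound (Section 6.1, inclusion 3). Exclusions 1 and 2 (pCO2, pH, lactate) are also judged on room air. Section 4.2.1.2 asks for a baseline SpO2 "by pulse oximetry on oxygen", and exclusion 11 applies to a reading on oxygen taken before Period 1 begins. Appendix B reproduces the WHO table, in which oxygen is a listed treatment when saturation is below 90%. The synopsis (Procedures) and Section 7.2 promise all patients WHO standard of care, including the availability of oxygen therapy.

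**The concern.** The children at issue are hypoxemic and in the group for whom the protocol's own WHO table prescribes oxygen. Saturation below 90% is also one of the signs in Appendix B that qualifies a child as having severe pneumonia, so the 85–89% range is central to the intended population. Section 2.1 itself says that the risk of death rises with the severity of hypoxemia.

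Read as a procedure, the sequence has a child at, say, 87% wait off oxygen through the consent discussion, a laboratory blood count, other tests and baseline recording. Most of that work can be done equally well with the child on oxygen. The exposure would fall on every child screened in that range, including those who are then found ineligible.

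**Working it through.** The protocol states no figure on this point, so the check is a comparison of its sections, with one sum to confirm that the affected group can be enrolled.

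**1. Order of events.**

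| Step | Source |
|---|---|
| Consent before any study procedure | 4.2.1.1; inclusion 5 |
| Screening list completed to decide eligibility | 4.2.1.1 |
| Baseline assessments once eligible | 4.2.1.2; Synopsis |
| Oxygen per standard of care | Synopsis; 4.1 |
| Randomization, then Period 1 | Synopsis; 4.1 |

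The final baseline item, SpO2 on oxygen, necessarily follows the start of oxygen. The rest of baseline and all of screening are placed before it. Glucose and the malaria test come before oxygen whether they are counted as baseline (Synopsis) or as screening (4.2.1.1, Appendix A).

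**2. Can a child at 85–89% enter?** Inclusion 3 admits the range. The remaining question is whether the SICK exclusion (score above 2.4) removes these children. Weights from Appendix C:

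- Age 12 to <60 months: SpO2 <90% (1.4) + age (0.3) = 1.7. Adding abnormal respiratory rate (0.4) and heart rate (0.2): 1.7 + 0.4 + 0.2 = 2.3, which is not above 2.4.
- Age ≥60 months: 1.4 + 0.0 = 1.4. With both rates abnormal: 1.4 + 0.4 + 0.2 = 2.0.
- One further item weighted 1.2 (blood pressure, temperature or capillary refill) would exclude: 1.7 + 1.2 = 2.9, or 1.4 + 1.2 = 2.6. Abnormal AVPU (2.0) would also exclude.

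So a child at 85–89% stays eligible on SICK unless a 1.2 or 2.0 item is also abnormal.

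**3. What truly needs room air?** The SpO2 reading for inclusion 3 and the capillary gas for exclusions 1 and 2 do, by their own wording. The SICK score uses SpO2 together with heart rate, respiratory rate, blood pressure, temperature, capillary refill and AVPU. If it is to describe one state of the child, those bedside signs belong with the room-air reading. Blood count, hemoglobin, malaria test, glucose, history, medication and mask size do not depend on whether the child is on oxygen.

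**4. Does another clause override the order?** The standard-of-care clauses promise that oxygen will be available but give no timing. No text that could be read says that oxygen starts at once below 90%, or that it may precede consent or screening. (Figure 4 and the consent document were not available to read.) Meanwhile, the room-air gas is listed as a screening assessment and so, as a study procedure, follows consent. That gives a site a positive reason to keep the child on air until then.

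**5. The sentence in Section 4.2.2.1.** It lists the start of oxygen under Period 1. The synopsis baseline paragraph, Section 4.2.1.2, exclusion 11, Section 7.2 and the Period 0 column of Appendix A all have the child on oxygen before Period 1.

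**The case against.** The best defense is that standard-of-care oxygen is not a study procedure and is nowhere made conditional on screening. The WHO commitment opens the synopsis procedures, ahead of the screening item, and is repeated in Section 7.2. These are hospitalized children under clinician care. Section 4.1 is a summary, the bullets in 4.2.1.1 and 4.2.1.2 set no order within each list, baseline values may be carried over from screening, and several items take little time at the bedside.

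Much of this stands. A reader might infer that the protocol orders oxygen to be withheld. It does not: nothing forbids earlier oxygen, and the WHO clauses make withholding an unlikely intention. A reader might also try to size the harm by counting the items listed before oxygen, or the share of screening blood that needs room air. Neither measures time off oxygen, so neither is used here.

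A reader might further infer from Section 4.2.2.1 that exclusion 11 cannot be applied. That would require a site to ignore the five other places that fix oxygen before Period 1. The sentence is simply misplaced.

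What the defense does not answer is that a specific sequence is stated more than once, while the general clause beside it is silent on timing.

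**Conclusion.** The point holds as a flaw in the stated sequence. Followed literally, it delays oxygen for children below 90% for the sake of tests that do not need room air, and the standard-of-care clauses do not settle the order. It does not show that any child would in fact be denied oxygen.

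The size cannot be given: the protocol states neither the proportion of screened children at 85–89% nor the duration of screening and baseline. The target of up to 20 patients does not bound the number exposed, because children who fail screening are affected too. At 90–93% the saturation threshold in Appendix B is not met, so the concern does not extend there.

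The conclusion assumes that sites would read the sequence in the synopsis and Section 4.1 as operational. It is worth correcting because the change is cheap and the benefit is to patient safety. The Section 4.2.2.1 sentence is a drafting correction only.

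**What to change.** In the synopsis, Section 4.1 and Section 4.2, state one order:

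1. When SpO2 is below 90%, standard-of-care oxygen is never delayed or removed for consent or any study procedure. This rule prevails if it conflicts with the steps below.
2. Take the room-air SpO2, the bedside SICK signs (heart rate, respiratory rate, blood pressure, temperature, capillary refill, AVPU) and the capillary gas first. Accept room-air values already recorded in routine admission care. Section 11.2 already has CRF data transcribed from medical records. Taking the SICK signs here avoids a score that mixes room-air SpO2 with signs measured on oxygen.
3. Start oxygen, then complete all other screening and baseline items on oxygen: blood count, hemoglobin, malaria test, glucose, history, medication and mask size.
4. Move the oxygen-start sentence from Section 4.2.2.1 to Section 4.2.1.2, ahead of the SpO2 on oxygen, to match exclusion 11 and Appendix A.

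The cost is rewording: no new test, visit or sample, and no changed threshold. There is a real downside. Exclusions 1 and 2 still require a room-air gas, so a child who needs oxygen before one can be drawn may not be enrollable. That could lower the share of enrolled children at 85–89% by an amount the protocol does not allow us to estimate.
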